3. DESCRIPTION OF DESIGN AND TRIAL POPULATION

3.1 OVERALL TRIAL DESIGN AND PLAN

This is a prospective, randomised, open label, blinded endpoint (PROBE), active comparator trial and the clinical endpoints are being adjudicated by an IAC in a blinded fashion.

This trial is designed to test the safety in NVAf patients that have undergone a successful PCI (elective or due to ACS) with stenting and were treatment naïve or were receiving oral anticoagulant treatment (either with warfarin, another VKA or other novel oral anticoagulant) before the procedure.

Patients will be consented and screened after undergoing a successful PCI. Randomisation will occur on local laboratory results taken at the screening visit or on standard of care local laboratory results taken within 7 days prior to screening; central laboratory samples must be taken at randomisation prior to first intake of study drug. Randomisation can occur up to 120 hours post PCI, however within 72 hours is preferable. Study drug should be administered between 6 hours after sheath removal and preferably within 72 hours post PCI, with haemostasis assured, however up to 120 hours post PCI is allowed.

Patients aged < 80 years will be randomly assigned to 110mg dabigatran etexilate b.i.d., 150mg dabigatran etexilate b.i.d. or warfarin in a 1:1:1 ratio for the duration of the trial.

Patients aged ≥ 80 years will be randomly assigned depending on their geographical location:

- Patients aged ≥ 80 years in the USA will be assigned to 110mg dabigatran etexilate b.i.d., 150mg dabigatran etexilate b.i.d. or warfarin in a 1:1:1 ratio
- All other patients aged ≥ 80 years outside of the USA will be assigned to 110mg dabigatran etexilate or warfarin in a 1:1 ratio.

In addition to their randomised treatment:

- All patients will receive either clopidogrel (75mg q.d.) or ticagrelor (90mg b.i.d), according to the local label, for at least 12 months after randomisation. Discontinuation of clopidogrel or ticagrelor or switching to ASA (≤ 100 mg q.d.) after 12 months of treatment is at the discretion of the Investigator
- Patients randomised to receive warfarin will receive ASA (≤ 100 mg q.d.) for either one month in patients with a bare metal stent BMS and for three months in patients with a DES.

For details of drug administration see [Section 4.1.4](#).

The study plan is detailed in [Figure 3.1: 1](#).

Proprietary confidential information.

© 2016 Boehringer Ingelheim International GmbH or one or more of its affiliated companies. All rights reserved.

This document may not - in full or in part - be passed on, reproduced, published or otherwise used without prior written permission.

[figure not shown]

Figure 3.1: 1 Study Plan

Prior to consent, the patient's antithrombotic treatment (i.e. ASA and anticoagulant use before and during PCI, use of clopidogrel or ticagrelor loading dose) should be managed as per local standard of care. The screening period will consist of one visit (Visit 1). The patients will be randomised at Visit 2. Screening and randomisation can be conducted on the same day. The treatment period will consist of between three and 10 visits (Visits 3-12). The trial is event driven and is designed to continue until approximately 500 patients with at least one MBE or CRNMBE (in total) occur. The last patient randomised will receive at least six months of treatment and patients recruited earlier remain in the study until the time point at which this last patient has reached at least six months. Any ongoing patient, at the time the required number of events is reached will be discontinued. Following completion of the treatment period, the patients will have a follow-up visit four weeks later.

The visits scheduled at 15, 21 and 27 months (Visits 8, 10 and 12) are to be conducted by telephone. Collection of AEs, outcome events (OE) (including bleeding) and use of concomitant medication will be made.

Blood sampling for a standard chemistry safety panel (including renal function and Liver Function Tests (LFTs)) will be collected at Visits 1, 2, 3, 5, 7 and End of treatment (EOT). In addition, samples for standard haematology safety panel will be taken at all clinic visits. All

Proprietary confidential information.

© 2016 Boehringer Ingelheim International GmbH or one or more of its affiliated companies. All rights reserved.

This document may not - in full or in part - be passed on, reproduced, published or otherwise used without prior written permission.

blood measurements (with the exception of INR and screening labs) will be performed by a central laboratory.

For further study procedure details see [Flow Chart](#).

The end of the trial is defined as “last patient out”, i.e. last visit completed by the last patient.

3.1.1 Administrative structure of the trial

An Executive Steering Committee, consisting of a small group of external experts and representatives from the Sponsor, will provide scientific leadership for the planning and conduct of the trial. A Steering Committee will also be formed, where in addition to these members, there will be representatives from every country participating in the trial. These committees will be chaired by the Coordinating Investigator. A charter describing the tasks and responsibilities of the Executive Steering Committee and Steering Committee will be developed.

Overall organisation will be overseen by an Operations Committee, consisting of representatives of the Sponsor and Harvard Clinical Research Institute. The Operations Committee will oversee the conduct and execution of the trial, coordinate the agenda for the Steering Committees and will be responsible for the day-to-day operations of the trial.

An independent DMC will monitor patient safety and the trial conduct. A detailed DMC charter will be written to govern the activities of this committee. The DMC analyses and operations will be formally separated from the Sponsor, the Investigators, the Steering Committees and the Operations Committee. All data (for both dabigatran etexilate and warfarin patients), both adjudicated and non-adjudicated will be reviewed by the DMC in an ongoing fashion.

An IAC will be established for the blinded adjudication of efficacy outcomes (e.g. death, stroke, MI, SE) as well as bleeding. An Adjudication Committee Charter, under which the principles of the PROBE design can be carried out, will govern their activities. The charter will provide detailed definitions of each endpoint and the processes by which adjudication will occur, including how blinding will be preserved.

The Coordinating Investigator is selected based on [REDACTED] expertise in this therapeutic area and reputation for being a [REDACTED] in [REDACTED] field. [REDACTED] will review and sign the clinical trial protocol (CTP) and relevant clinical trial report (CTR).

Physicians (e.g. cardiologists, interventionalists) managing anticoagulation may be Investigators for this trial.

An Interactive Response Technology (IRT) will perform the randomisation of patients and ensure appropriate distribution of trial medication to trial sites during the course of the trial.

A central laboratory will perform all protocol specified blood analyses with the exception of INR and screening measurements.

Proprietary confidential information.

© 2016 Boehringer Ingelheim International GmbH or one or more of its affiliated companies. All rights reserved.

This document may not - in full or in part - be passed on, reproduced, published or otherwise used without prior written permission.

All trial-related documents will be stored in the Clinical Trial Master File at each individual Boehringer Ingelheim (BI) Operative Unit (OPU) in accordance with standard operating procedures.

3.2 DISCUSSION OF TRIAL DESIGN, INCLUDING THE CHOICE OF CONTROL GROUP(S)

TAT, comprising of VKA, clopidogrel and ASA, is the current standard treatment to prevent post-PCI stent thrombosis and the recommendation by multiple international guidelines (consensus document of the European Society of Cardiology Working Group on Thrombosis that was endorsed by the European Heart Rhythm Association (EHRA) and the European Association of Percutaneous Cardiovascular Interventions (EAPCI) [[P10-07397](#)]; and the North American Consensus Document on Antithrombotic therapy in patients with AF undergoing coronary stenting [[P11-09369](#)]). The WOEST results have been reflected in some of the recent guidelines for NVAf patients undergoing PCI with stenting [[P14-05384](#), [P14-12794](#), [P16-02545](#)] which recommend to consider the use of DAT in certain patients. However, data from clinical trials concerning the possibility of implementing DAT regimens with dabigatran etexilate and other new NOACs in this setting are needed.

Therefore, an active control group is required for any study in patients who have undergone PCI with stenting. Warfarin, the most widely used VKA, was chosen as the active control in this study.

The trial is event driven; therefore all patients will remain in the trial until the required number of events have occurred. Individual patient participation will vary from approximately 6 months to 2.5 years or longer (estimated average duration 18 months).

Double-blind, double-dummy trials in anticoagulation have limitations due to potential unavoidable deviations from routine clinical procedures [[R08-4453](#)]. This trial will use the PROBE design. The PROBE approach has been used in several trials of anticoagulation comparing against VKAs, e.g. in patients with AF.

The following procedures will be implemented to reduce the potential for bias in the reporting and assessment of primary and secondary events.

1. Clearly defined objective outcomes:

The primary and secondary outcomes of the study are clinically relevant events for which objective documentation will be obtained. Standard, widely accepted definitions are to be used that rely on objective documentation.

2. Blinded IAC:

All OEs will be adjudicated by blinded adjudication experts. Blinding of all event documentation will be performed by trained specialists. The role of the IAC will be to oversee and perform the blinded adjudication of all outcome events. This Committee will report to the Executive Steering Committee and DMC.

3. Bleeding Questionnaire:

Proprietary confidential information.

© 2016 Boehringer Ingelheim International GmbH or one or more of its affiliated companies. All rights reserved.

This document may not - in full or in part - be passed on, reproduced, published or otherwise used without prior written permission.

A questionnaire querying patients for signs and symptoms of bleeding will be administered at each visit. The goal is to reduce the possibility of under-reporting of events. All symptoms will be evaluated and if potentially consistent with an outcome event will be referred to the IAC.

4. Review of Data for Clinical Events:

Any AE that indicates potential loss of neurological function, such as unilateral weakness, loss of vision or sensory disturbance will trigger a request for more information from the centre for event adjudication if potentially consistent with an outcome event. Any decrease in haemoglobin of >2g/dL will be similarly investigated.

5. Data Handling:

Patients will be randomly allocated to the treatment arms via IRT. Wherever feasible, data management will be undertaken without knowledge of patient treatment allocation. Special procedures to handle data with the potential for unblinding, such as INRs, will be specified. By treatment data tabulations will not be reviewed during the course of the trial and the data management personnel will not have access to the randomisation code.

By implementing these appropriate measures to avoid bias, the PROBE design is an acceptable [[R14-0530](#)] and preferred approach for this study.

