- CABG related MI is arbitrarily defined by elevation of cardiac biomarker values ($> 10 \times$ 99th percentile URL) in patients with normal baseline cTn values (\leq 99th percentile URL). In addition, either (i) new pathological Q waves or new LBBB, or (ii) angiographic documented new graft or new native coronary artery occlusion, or (iii) imaging evidence of new loss of viable myocardium or new regional wall motion abnormality.

Criteria for fatal MI

Death due to Acute MI refers to a death by any cardiovascular mechanism (e.g., arrhythmia, sudden death, heart failure, stroke, pulmonary embolus, peripheral arterial disease) ≤ 30 days after a MI related to the immediate consequences of the MI, such as progressive heart failure or recalcitrant arrhythmia. Acute MI (for criteria see above) should be verified to the extent possible by the diagnostic criteria outlined for acute MI or by autopsy findings showing recent MI or recent coronary thrombosis. Death resulting from a procedure to treat a MI (e.g.

Proprietary confidential information.

© 2016 Boehringer Ingelheim International GmbH or one or more of its affiliated companies. All rights reserved.

This document may not - in full or in part - be passed on, reproduced, published or otherwise used without prior written permission.

PCI, CABG), or to treat a complication resulting from MI, should also be considered death due to acute MI [[R15-0010](#)].

Silent MI

Silent myocardial infarction will be retrospectively diagnosed by the appearance of significant new Q-waves on an ECG performed after randomisation. In such cases, the date of the event is recorded as the midpoint between the ECG with new Q-waves and the prior normal ECG.

Criteria for prior MI [[R13-4872](#)]:

Any one of the following criteria meets the diagnosis for prior MI:

- Pathological Q waves with or without symptoms in the absence of non-ischaemic causes
- Imaging evidence of a region of loss of viable myocardium that is thinned and fails to contract, in the absence of a non-ischaemic cause
- Pathological findings of a prior MI.

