5.2.4 Electrocardiogram

All ECGs will be collected on standardised devices and stored at a central digital database provided by a central ECG service. At each visit as indicated in the [Flow Chart](#) a 12-lead ECGs (I, II, III, aVR, aVL, aVF, V1 - V6) will be recorded. The ECGs will be evaluated by the Investigator or a designate for immediate investigation or treatment. In addition, the central ECG vendor will provide manual reading results which will be communicated to the Investigator for [REDACTED] further judgment and will be stored in the central database of the vendor.

Additional ECGs recorded outside the Investigator's facilities may be collected by the Investigator and transferred to the central database for safety reasons.

Upon receipt of an alert from the ECG vendor, the Investigator or designate is expected to review, sign and date the findings, record their clinical judgement in the source documents. Agreement with the findings should result in a reported OE or (S)AE, if judged to be clinically relevant. If the Investigator does not agree with the ECG reviewer's findings, a note should be made in the source regarding the review of the alert. Clinically relevant changes in the ECG will be reported as AEs.

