7.8.4 ECG

ECGs will be evaluated centrally by an external vendor. Summary statistics will be displayed at baseline and further summaries will be produced for the number of patients who develop significant Q waves, atrial flutter, atrial fibrillation, ST segment changes and other changes.

In addition, ECG abnormalities will be summarised in the AE or baseline conditions tables.

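### Section 5.2.4 passes centrally read Q waves through the unblinded investigator, and neither document states a direct route to the blinded adjudicators, so silent MI can be filtered before it counts in Steps 3 and 5

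*Protocol*

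**What the plan says.** Protocol 3.2 lists measures against bias in the reporting and assessment of events. Item 2 is blinded adjudication: "All OEs will be adjudicated by blinded adjudication experts". Item 4 adds data-review triggers that prompt a request for adjudication material. It names two: "Any AE that indicates potential loss of neurological function, such as unilateral weakness, loss of vision or sensory disturbance", and a laboratory trigger, "Any decrease in haemoglobin of >2g/dL will be similarly investigated". Item 3 is a questionnaire about bleeding. None of these concerns ECG findings.

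Protocol 5.1.2.2 places silent MI under the MI endpoint: "Silent myocardial infarction will be retrospectively diagnosed by the appearance of significant new Q-waves on an ECG performed after randomisation". ECGs are scheduled at baseline and every six months until end of treatment (Flow Chart, footnote 10).

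Protocol 5.2.4 describes what happens to the tracing: "the central ECG vendor will provide manual reading results which will be communicated to the Investigator", and the reading is stored in the vendor's database. The investigator then reviews any alert. On agreement the rule is "Agreement with the findings should result in a reported OE or (S)AE, if judged to be clinically relevant". On disagreement, "a note should be made in the source regarding the review of the alert". The IAC is not mentioned.

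Under Protocol 5.2.2.2 the investigator or a designee enters outcome events in the eCRF, and the sponsor forwards them to the IAC. SAP 7.5.2 analyses only positively adjudicated events. SAP 7.8.4 uses the central ECG data descriptively: "further summaries will be produced for the number of patients who develop significant Q waves".

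**The concern.** A trial with open treatment and blinded endpoint review is protected to the extent that people who know the arm do not decide which candidate events reach the blinded committee. Symptomatic MI usually leaves independent traces such as an admission and biomarkers. Silent MI may have only the ECG. For that subtype, the rule in 5.2.4 lets an unblinded opinion come before the blinded one.

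At stake are the two confirmatory efficacy tests: Step 5 (DTE, both dabigatran doses combined against warfarin-TAT) and Step 3 (the same plus unplanned revascularisation). Filtering that is equal across arms costs events. Filtering that differs by arm moves the hazard ratio. Steps 3 and 5 are non-inferiority tests, so a shift favouring dabigatran would make a false claim of non-inferiority more likely.

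**Working it through.** **Tracing the route.**
1. The investigator knows the allocation (Protocol 4.1.5.1).
2. The central reading goes to the investigator and to the vendor's database (5.2.4). By contrast, central laboratory results are loaded directly into the trial database (5.2.3).
3. An outcome event exists for the IAC once the site enters it (5.2.2.2). Under 5.2.4 that follows agreement with the reading. As worded, an agreed finding could also be filed as an (S)AE, which the neurological trigger in 3.2 item 4 would not pick up.
4. The SAP adjudication summary and the sensitivity analyses on investigator-reported events (7.4, 7.5.2) start from what the site reported. A Q wave that the site declined is in neither.
5. The Q-wave summary in SAP 7.8.4 is not linked to adjudicated MI in the available text.

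**The plan's own figure.** The only stated design figure is 83.6% power for the bleeding test (Protocol 7.6). It reproduces: Φ(√(334 × 0.25) × ln 1.38 − 1.96) = Φ(2.943 − 1.960) = 83.7%. No corresponding figure is given for DTE or MI.

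**Illustration.** Every DTE input here is an assumption.
- *s* is the share of patients with a DTE whose only DTE is a silent MI: 2%, 5% or 10%.
- *d*(DE) and *d*(W) are the fractions of silent MIs not referred in the combined dabigatran arms and in the warfarin arm.
- Total DTE is 200 to 400, with 2:1 allocation. This is approximate, because elderly patients outside the USA are randomised to two arms only.
- The true hazard ratio equals 1.38, the margin in SAP 7.4.

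The observed hazard ratio is the true one multiplied by (1 − *s·d*(DE)) / (1 − *s·d*(W)). For *s* = 10% and 50% against 25% declined, this is 0.950 / 0.975 = 0.974.

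| Declined, DE / warfarin | s = 2% | s = 5% | s = 10% |
|---|---|---|---|
| 50% / 50% | 1.000 | 1.000 | 1.000 |
| 50% / 25% | 0.995 | 0.987 | 0.974 |
| 75% / 25% | 0.990 | 0.975 | 0.949 |
| 25% / 50% | 1.005 | 1.013 | 1.026 |
| 25% / 75% | 1.010 | 1.026 | 1.054 |

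The standard error of the log hazard ratio is about 1/√(E × 2/3 × 1/3), which is 0.150 at E = 200 and 0.106 at E = 400. The one-sided type I error at the margin is Φ(shift/SE − 1.96), where shift is the size of the log multiplier and events already filtered out are removed from E:
- 50% / 50%: stays at 0.025. Retained events fall from 200 to between 198 and 190, or from 400 to between 396 and 380.
- 50% / 25%: 0.027 to 0.043.
- 75% / 25%: 0.029 to 0.070.
- The reversed patterns bring it below 0.025 and work against showing non-inferiority.

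As a bound, declining every silent MI in the dabigatran arms and none in the warfarin arm at *s* = 10% gives a multiplier of 0.90.

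**The case against.** **The charter may close the gap.** Protocol 3.1.1 leaves the adjudication process to the Adjudication Charter, where a central-ECG referral rule could well sit. Some SAP sections are also withheld. This stands: a reader might infer that silent MI cannot reach the IAC without the investigator, but the documents support only the statement that no other route is given in the available text.

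**Disagreement is not said to close the matter.** It is tempting to say that the process ends with the source note. Section 5.2.4 is silent on what follows. The reading stays in the vendor's database, monitors review source documents (8.3.2), and the DMC sees adjudicated and non-adjudicated data (3.1.1). This stands as a limit, although none of these is a stated referral to the IAC.

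**Section 3.2 is not contradicted.** Outcome events that are reported are adjudicated, item 4 does not call its triggers exhaustive, and site entry of events is an open part of the design. This also stands. The rule at issue is in 5.2.4; 3.2 is the safeguard that it weakens.

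**Discretion is narrower than it looks.** All MIs are outcome events (5.2.2.2), silent MI has no relevance test (5.1.2.2), and the clinical-relevance condition in 5.2.4 can be read as attaching to the (S)AE alternative. On that reading, agreement obliges reporting, and what remains is disagreement with the reading. This narrows the gap but does not close it.

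**The size is assumed.** The endpoints are time to first event. A patient with an unreferred silent MI and another DTE still counts, so treating every silent MI as a lost event overstates the effect. This stands.

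**Conclusion.** The point holds as a stated reporting rule that allows unblinded filtering of one MI subtype before blinded adjudication, with no compensating route in the available protocol or SAP. It touches Steps 3 and 5 only. The primary bleeding comparisons and their superiority tests (Steps 1, 2, 4 and 6) do not depend on it.

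A reader might conclude that the efficacy comparisons are biased toward non-inferiority. The documents do not support that: they contain nothing on how often investigators disagree, or on whether disagreement would differ by arm. Equal filtering leaves the hazard ratio unbiased. Unequal filtering could go either way and, over the ranges above, moves it by about 0.5% to 5%, at most about half a standard error (ln 0.949 = −0.053 against 0.106). All of this rests on assumed shares and decline rates, and on the charter containing no referral rule. It is worth correcting because the correction is cheap, not because a large distortion has been shown.

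**What to change.** Amend two places in the protocol and align the Adjudication Charter:
- **3.2 item 4:** add a third trigger. Any new significant Q wave on the central reading of an ECG taken after randomisation is sent to the blinded IAC by the sponsor, whether or not the investigator agrees.
- **5.2.4:** state that investigator disagreement is recorded and does not stop referral. The IAC then applies the MI definition in 5.1.2.2.

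If the charter already contains such a rule, 5.2.4 should say so.

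If conduct is too advanced for this, reconcile central-reading Q waves with adjudicated MI in a blinded manner before database lock. Then report a sensitivity analysis for Steps 3 and 5 that adds the unmatched Q waves as MI, dated by the midpoint convention in 5.1.2.2.

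The ECGs and readings are already collected. The cost is the wording change, additional adjudication packets and some negative referrals.
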